6.3.3.4. Presentation of Results

No formal inferential statistics (p-values) will be derived.

Continuous parameters will be summarized by means of descriptive statistics (including 90% CI of the mean change) by parameter, treatment group and analysis window. Actual values, change from baseline and percent changes from baseline will be tabulated separately.

Profile line plots by subject of all actual observed values using relative day (ADY) will be presented by treatment group. Graphs of the mean (+- SE) actual values over time and of the mean (+- SE) change from baseline and percent change from baseline will be presented. A line plot by subject of the change from baseline will also be provided by treatment group.

The analysis of abnormalities will focus on assessments reported during the treatment period. Results reported during the screening or post-treatment (if defined) period will only be listed.

Abnormalities of the actual values will be presented as shift tables of the worst-case abnormality versus the baseline abnormality. The table will be created per parameter, treatment group and analysis period.

A frequency table of the number (percent) of subjects with treatment-emergent worst-case abnormalities and the worst change per parameter, treatment group and analysis period will be presented.

A frequency table per treatment group and time point of the ECG interpretations as recorded in the case report form (CRF) will be provided.

A Listing will be provided along with abnormality.

6.3.4. Vital Signs

6.3.4.1. Available Data

The following vital signs parameters will be analyzed: weight (kg), BMI (kg/m²), diastolic and systolic blood pressure (mmHG), pulse rate (beats/min) and body temperature (C).

6.3.4.2. Derivation Rules

Not applicable.

6.3.4.3. Abnormalities

Vital signs data will be categorized according to the cutoffs provided in the SAP [Appendix II](#).

6.3.4.4. Treatment-Emergent Principle

A post-baseline abnormality class L or H is defined as treatment-emergent when it differs from the abnormality class at baseline. If the baseline result is missing, a post-baseline abnormality L or H will be considered as treatment-emergent.

An abnormal category for change from baseline is always treatment-emergent.

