6.3.2.6. Treatment-Emergent Principle

Toxicity Grades

A post-baseline toxicity grade 1, 2, 3 or 4 is defined as treatment-emergent when higher than the toxicity grade of the baseline result or when there is a change in direction (from H to L or from L to H). If the baseline result is missing, a post-baseline toxicity grade 1, 2, 3 or 4 will be considered as treatment-emergent.

Non-graded Abnormalities

A post-baseline non-graded abnormality class L or H is defined as treatment-emergent when it differs from the abnormality class of the baseline result. If the baseline result is missing, a post-baseline abnormality L or H will be considered as treatment-emergent.

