6.3.3.3. Abnormalities

The actual analysis values and changes from baseline of the QT and QTcF parameters will be categorized into the abnormality classes as defined in the SAP [Appendix II](#).

Worst-Case Abnormality

The worst-case post-baseline categorized actual analysis value and the worst-case categorized change from baseline for QT and QTcF will be determined per subject, per parameter, and for each analysis period, using all non-missing post-baseline records (including unscheduled and FU visits).

The worst-case categorized actual analysis value is the category corresponding to the highest post-baseline actual value. In case of several equal highest post-baseline actual values, the earliest occurrence will be taken for the analyses and will be flagged in the listings.

The worst-case change from baseline is the category corresponding to the largest increase (positive change) from baseline. In case of several equal largest increase from baseline, the earliest occurrence will be taken for the analyses and will be flagged in the listings.

Treatment-Emergent Abnormalities

Actual value: An abnormal post-baseline abnormality is defined as treatment-emergent when the abnormality is worse compared to the abnormality at baseline or when there is a change in direction (from H to L or from L to H). When the baseline value is missing, post-baseline abnormalities are considered as treatment-emergent.

An abnormal category for change from baseline is always treatment-emergent.

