Any laboratory parameter with treatment-emergent (i.e., worsening from baseline) abnormalities of grade 2 or above (ie, H2/L2 or higher/lower) should be considered a 'marked laboratory abnormality'. Marked laboratory abnormalities should be described in a corresponding section of the CSR as per ICH E3 guidance, section 12.4.2.3.

APPENDIX II: Vital Signs and Electrocardiogram grading**Table 4 Gradings for Vital Signs and Electrocardiogram Parameters**

Parameter	L1	L2	L3	L4	H1	H2	H3	H4
Systolic blood pressure (mmHg)	<90	<60	NA	NA	NA	≥140	≥160	≥180
Diastolic blood pressure (mmHg)	<60	<45	NA	NA	NA	≥90	≥100	≥120
Heart rate (bpm)	<60	<50	<40	NA	>100	>115	>130	NA
Body temperature (°C)	NA	<35	NA	NA	>38	NA	NA	NA
Respiratory rate (breaths per minute)	<12	NA	NA	NA	>20	NA	NA	NA
O ₂ saturation (%)	<95	<90	NA	NA	NA	NA	NA	NA
Weight	≥7% decrease from baseline	NA	NA	NA	≥7% increase from baseline	NA	NA	NA
QTc interval on ECG (ms)	NA	NA	NA	NA	>450	>480	>500	NA
QTc change from baseline (ms)	NA	NA	NA	NA	NA	>30	>60	NA
PR interval on ECG (ms)	<110	NA	NA	NA	>200	NA	NA	NA

Parameter	L1	L2	L3	L4	H1	H2	H3	H4
QRS complex on ECG (ms)	<60	NA	NA	NA	>120	NA	NA	NA

Source: FRM-MED-005/006, valid on 08JUL2020.

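### The vital-sign treatment-emergent rule in SAP 6.3.4.4 compares ungraded classes on a graded scale, so worsening within an already abnormal class is left out of the treatment-emergent table

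*SAP*

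**What the plan says.** SAP 6.3.4.3 sends the reader to Appendix II for the categories: "Vital signs data will be categorized according to the cutoffs provided in the SAP". That table is graded. With columns running L1 to L4 and then H1 to H4, the systolic row is "Systolic blood pressure (mmHg) <90 <60 NA NA NA ≥140 ≥160 ≥180". Diastolic pressure and heart rate are graded in the same way.

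SAP 6.3.4.4 has three sentences. The first sets the rule: "A post-baseline abnormality class L or H is defined as treatment-emergent when it differs from the abnormality class at baseline". The second treats any low or high result as treatment-emergent when baseline is missing. The third says: "An abnormal category for change from baseline is always treatment-emergent".

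SAP 6.3.4.5 takes the category of the highest post-baseline value as the worst case. SAP 6.3.4.6 uses it in a shift table against baseline and in a frequency table of treatment-emergent worst-case abnormalities by treatment group.

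Elsewhere the SAP uses two kinds of rule:

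- Graded laboratory tests (6.3.2.6): a grade "is defined as treatment-emergent when higher than the toxicity grade of the baseline result or when there is a change in direction".
- ECG (6.3.3.3): treatment-emergent "when the abnormality is worse compared to the abnormality at baseline or when there is a change in direction".
- Non-graded laboratory results (6.3.2.6): "A post-baseline non-graded abnormality class L or H is defined as treatment-emergent when it differs from the abnormality class of the baseline result".

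**The concern.** The vital-sign rule is nearly word for word the non-graded laboratory rule, yet the data it acts on are graded. It sets no condition on severity and does not say whether class means low/normal/high or the Appendix II grade. On the first reading, a subject already abnormal at baseline cannot become treatment-emergent in the same direction, however far the value moves. On the second, a move to a milder abnormal grade counts just as a move to a worse one does.

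Safety and tolerability is a secondary objective, and blood pressure and heart rate form part of that picture. Two programmers could follow 6.3.4.4 faithfully and produce different tables, and neither table would isolate worsening from baseline.

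**Working it through.** No figure in the plan needs reproducing; the check is to apply the rules to the cutoffs.

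**Inputs.** Systolic grades from Appendix II: L2 <60, L1 <90, H2 ≥140, H3 ≥160, H4 ≥180 mmHg; otherwise normal (N). The rule of 6.3.4.4 is applied under its two readings and compared with the graded laboratory and ECG rule (worse than baseline, or a change of direction).

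**Is the result treatment-emergent?**

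| Baseline → later SBP | Grades | 6.3.4.4, class = L/N/H | 6.3.4.4, class = grade | Worse or change of direction |
|---|---|---|---|---|
| 120 → 145 | N → H2 | yes | yes | yes |
| 145 → 150 | H2 → H2 | no | no | no |
| 145 → 165 | H2 → H3 | **no** | yes | yes |
| 145 → 185 | H2 → H4 | **no** | yes | yes |
| 165 → 145 | H3 → H2 | no | **yes** | no |
| 185 → 145 | H4 → H2 | no | **yes** | no |
| 85 → 145 | L1 → H2 | yes | yes | yes |
| 185 → 85 | H4 → L1 | yes | yes | yes |

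**All pairs of systolic grades.** The L/N/H reading misses four worsenings: L1→L2, H2→H3, H2→H4 and H3→H4. The graded reading counts four improvements: L2→L1, H3→H2, H4→H2 and H4→H3. The number follows from the scale: k grades in one direction give k(k−1)/2 ordered worsenings, so 2 low and 3 high grades give 1 + 3 = 4. Diastolic pressure has the same structure (4). Heart rate, with 3 low and 3 high grades, gives 3 + 3 = 6.

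**Does the third sentence of 6.3.4.4 help?** It covers categories of change from baseline. Among vital signs, Appendix II defines such a category only for weight. It does nothing for blood pressure or heart rate.

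**Effect of 6.3.4.5.** The table uses the highest post-baseline value. Under the graded reading, a subject with baseline SBP 185 is therefore wrongly counted only if the highest later value falls in 140-179 (H2 or H3). The same selection works against low grades: SBP of 85 at one visit and 130 at another gives a worst case of 130, which is normal. By contrast, 6.3.2.7 selects the laboratory worst case separately for increases and decreases.

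**Size per subject.** 1/15 = 6.7 percentage points in the GLPG3970 arm and 1/10 = 10 points in the placebo arm.

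**Subjects open to the error.** The readable eligibility criteria set no blood-pressure limit, and the documents give no prevalence of raised pressure at baseline. If 10% to 40% had SBP ≥140 or DBP ≥90 (an assumption), that would be 0.10 × 25 = 2.5 to 0.40 × 25 = 10 subjects. These are subjects in whom the rule could fail. An actual miss also requires a rise in grade.

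**The case against.** The strongest defence is that 6.3.4.4 means what it says: low or high, compared with low, normal or high. It matches the non-graded laboratory wording, and where the SAP means grades it says so. On that reading the table lists newly abnormal subjects, which is a recognisable convention, and a fall from 185 to 145 is not counted. This is the more natural reading. It removes the false count but confirms the missed worsening, and it leaves unexplained why vital signs, graded under 6.3.4.3, lack the rule given to graded laboratory tests and ECG. The version history records that 6.3.4.5 was changed to match ECG and lists no matching change to 6.3.4.4.

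The second defence is that worsening is visible elsewhere. Actual values and changes from baseline are summarised with 90% confidence intervals, values are listed, shift tables are planned, and protocol 8.5.4 has clinically significant abnormal values recorded as adverse events. This largely stands, although the shift table shows H2 to H4 only if it is built on grades. These outputs limit the harm but do not correct the treatment-emergent table.

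The third is that age below 65, BMI of 18 to 32 and the exclusion of poorly controlled cardiac or renal disease may make raised baseline pressure uncommon. That is fair, and it is why no expected number of errors is claimed.

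**Conclusion.** The point holds in a limited form. On the natural reading, 6.3.4.4 leaves worsening within an abnormal class out of the treatment-emergent table of 6.3.4.6. On the alternative reading, it counts improvements that remain abnormal. The rule should be corrected, but only one descriptive table and the flags derived from it are affected. The primary endpoint and the signal-detection framework are untouched, and no p-values are planned for vital signs.

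Three stronger conclusions that a reader might draw are not supported:

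- That the plan reports improvement as harm. This needs the less natural graded reading and, in the 185 mmHg example, a highest post-baseline value that stays within 140-179.
- That a rise such as 145 to 185 would go unseen. The other outputs and adverse event recording would show it.
- That 2 to 10 of the 25 subjects would be misclassified. That range rests on an assumed prevalence and counts subjects exposed to the rule, not errors.

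**What to change.** Make two edits.

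1. Replace the first two sentences of 6.3.4.4 with: *A post-baseline Appendix II grade is treatment-emergent when it is worse than the baseline grade in the same direction, or when the direction changes (H to L or L to H); if baseline is missing, any post-baseline abnormal grade is treatment-emergent.* Count a value inside the thresholds as grade 0, as 6.3.2.3 does for laboratory tests. Keep the third sentence, because the weight category depends on it.
2. In 6.3.4.5, select the worst case by direction: the highest value for H grades and the lowest for L grades, in line with the by-direction laboratory rule of 6.3.2.7. Without this, the low-side part of the new rule would have little effect in the table.

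Under these edits 145 to 185 is treatment-emergent, 185 to 145 is not, and 185 to 85 still is. The cost is a few sentences and matching changes to the vital-sign frequency and shift tables, where a subject may then appear once under L and once under H. The logic is already specified for laboratory tests and ECG, and no new data are needed.

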6.3.4.5. Worst-Case Abnormality

The worst-case post-baseline categorized actual analysis value will be determined per subject, per parameter and for each analysis period, using all non-missing post-baseline records (including unscheduled and FU visits).

The worst-case categorized actual analysis value is the category corresponding to the highest post-baseline actual value. In case of several equal highest post-baseline actual values, the earliest occurrence will be taken for the analyses and will be flagged in the listings.

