4.3.2. Analysis Periods

For treated subjects, adverse events and assessments will be allocated to analysis periods according to

Table 1.

Table 1 Analysis Periods

Analysis Period	Start Analysis Period	End Analysis Period
Screening	Date of signing the ICF, with 00:00 added as time part	Date (time) of first IP administration - 1 minute
Treatment	Date (time) of first IP administration.	Study termination date (i.e. date of last contact), with 23:59 added as time part

The last analysis period will always end on the date of last contact.

For every subject, all assessments performed and all events occurring during the study are expected to have a (start) date (/time) between the date of informed consent (IC) signature and the last contact date. Obvious exemptions are historical records like medical history or concomitant therapies having started before the study.

Assessments and events will be allocated to one of these analysis periods by incidence, meaning placing the record (start) date and time between the matching start and end dates and times of the subject's own analysis periods, assuming completeness of all dates and times, or further determined by the presence of timing indicators such as tick boxes flagging AEs starting before/after first IP administration, or by worst-case considerations for AEs if needed. For the parameters for which the time of assessment was not planned to be collected, their assessment on the day of first IP administration will be considered as baseline and will be reported under the 'Screening' analysis period with the exception of AEs.

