6.3.4.6. Presentation of Results

No formal inferential statistics (p-values) will be derived.

Continuous parameters will be summarized by means of descriptive statistics (including 90% CI of the mean change) by parameter, treatment group and analysis window. Actual values, change from baseline and percent change from baseline will be tabulated separately.

Graphs of the mean (+- SE) actual values over time and of the mean (+- SE) change from baseline, and percent changes from baseline will be presented.

The analysis of abnormalities will focus on assessments reported during the treatment period. Results reported during the screening or post-treatment (if defined) period will only be listed.

Abnormalities of the actual values will be presented as shift tables of the worst-case abnormality versus the baseline abnormality. The table will be created per parameter (and position if applicable), treatment group and analysis period.

A frequency table of the number (percent) of subjects with treatment-emergent worst-case abnormalities per parameter, treatment group and analysis period will be presented.

A listing will be provided along with abnormality.

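### Vital signs: taking only the highest post-baseline value as the worst case hides almost every low-grade abnormality from the two abnormality tables

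*SAP*

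**What the plan says.** - **Parameters.** SAP 6.3.4.1 analyses weight, BMI, "diastolic and systolic blood pressure (mmHG), pulse rate (beats/min) and body temperature (C").
- **Grading.** SAP 6.3.4.3: "Vital signs data will be categorized according to the cutoffs provided in the SAP" Appendix II. Table 4 there, headed "Gradings for Vital Signs and Electrocardiogram Parameters", has low as well as high columns for blood pressure, heart rate and temperature. It grades weight on a change of 7% or more from baseline in either direction.
- **Treatment emergence.** SAP 6.3.4.4 lets a class of L or H be treatment-emergent if it is not the baseline class.
- **Worst case.** SAP 6.3.4.5: "The worst-case categorized actual analysis value is the category corresponding to the highest post-baseline actual value". It is found per subject, parameter and analysis period, "using all non-missing post-baseline records (including unscheduled and FU visits"). The tie rule also refers only to highest values.
- **Period.** SAP 4.3.2 has one analysis period after first dose, Treatment, which ends at "Study termination date (i.e. date of last contact), with 23:59 added as time part".
- **Outputs.** SAP 6.3.4.6: "Abnormalities of the actual values will be presented as shift tables of the worst-case abnormality versus the baseline abnormality", and "A frequency table of the number (percent) of subjects with treatment-emergent worst-case abnormalities per parameter, treatment group and analysis period will be presented".

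**The concern.** The SAP defines low grades, says that they can be treatment-emergent, and then picks the value to tabulate with a rule that almost never selects them. No other section gives vital signs a lowest-value rule.

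Pulse, blood pressure and temperature can be abnormal in both directions. A fall in pressure or pulse on treatment disappears from both tables as soon as the subject has one non-low reading anywhere after first dose. That reading may be an unscheduled re-check made because the first value was low, or the follow-up visit after treatment has stopped.

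The version history suggests the cause: the section was rewritten to match the ECG section. The ECG rule in 6.3.3.3 covers QT and QTcF, and Appendix II grades QTc upward only, so the highest value is the right choice there. That does not carry over to two-sided parameters.

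Two related gaps sit beside this one:

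- **Weight.** It is graded on change from baseline, and 6.3.4.5 has no worst-case rule for change. The ECG section has one.
- **Meaning of class in 6.3.4.4.** It can mean direction, as in the non-graded laboratory rule (6.3.2.6), or Appendix II grade, as in the ECG section (6.3.3.3). The two readings give different treatment-emergent counts.

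**Working it through.** The plan states no figure to reproduce. The check is of the rule against the Appendix II cutoffs.

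**Inputs (SAP Appendix II, Table 4; parameters graded on actual value)**

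| Parameter | Low cutoffs | High cutoffs |
|---|---|---|
| Systolic (mmHg) | L1 <90, L2 <60 | H2 ≥140, H3 ≥160, H4 ≥180 |
| Diastolic (mmHg) | L1 <60, L2 <45 | H2 ≥90, H3 ≥100, H4 ≥120 |
| Heart rate (bpm) | L1 <60, L2 <50, L3 <40 | H1 >100, H2 >115, H3 >130 |
| Temperature (°C) | L2 <35 | H1 >38 |

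Low cutoffs: 2 + 2 + 3 + 1 = 8. High cutoffs: 3 + 3 + 3 + 1 = 10. So 8 of 18 are low. This applies the heart-rate row to the pulse rate of 6.3.4.1, which the SAP does not say outright. Without that row: low 2 + 2 + 1 = 5, high 3 + 3 + 1 = 7, so 5 of 12.

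**Step 1: logic.** A low grade is a value below a cutoff c. The maximum of a set is below c if and only if every member is. The rule therefore returns a low grade only when all readings are low, and then returns the mildest low grade seen. Enumerating all four-reading profiles on grids spanning the cutoffs (6,561 for systolic, 4,096 each for diastolic and heart rate, 256 for temperature) gave no exception.

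**Step 2: patterns.** The schedule (SAP Table 1) gives a completer four post-baseline vital-sign readings: Days 15, 29, 43 and 57. Low/not-low patterns with at least one low: 2^4 − 1 = 15. Tabulated as low: 1 (all four low).

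**Step 3: examples (invented readings)**

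| Readings | Rule as written (highest) | Lowest value |
|---|---|---|
| Systolic 118, 84, 112, 121 | 121: normal | 84: L1 |
| Diastolic 72, 44, 70, 75 | 75: normal | 44: L2 |
| Pulse 72, 38, 70, 74 | 74: normal | 38: L3 |
| Pulse 72, 38, 70, 104 | 104: H1 only | 38: L3 |
| Pulse 52, 38, 55, 58 | 58: L1 | 38: L3 |
| Pulse 48, 45, 47, then 66 at follow-up | 66: normal | 45: L2 |

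In the last row all three on-treatment readings are L2, and the follow-up reading alone removes them.

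**Step 4: illustration under an assumption.** Suppose four independent readings, each low with probability p. Then P(at least one low) = 1 − (1 − p)^4 and P(tabulated low) = p^4.

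| p | At least one low | Tabulated low |
|---|---|---|
| 0.1 | 0.344 | 0.0001 |
| 0.2 | 0.590 | 0.0016 |
| 0.5 | 0.938 | 0.0625 |

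The values of p are assumed. Readings within a subject are correlated, which would narrow the gap, so this shows direction only.

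**Step 5: scale of one subject.** With 15 and 10 subjects planned, one missed subject moves a displayed percentage by 1/15 = 6.7 points (GLPG3970) or 1/10 = 10 points (placebo).

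**Step 6: weight.** If the highest-value rule is applied to weight anyway, the highest weight is also the largest increase, so the H grade is found. A loss of 7% or more appears only if every post-baseline weight is at least 7% below baseline.

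**Step 7: emergence readings.** Systolic 145 is H2 and 185 is H4. If class means direction, 145 at baseline and 185 later is H to H, so not treatment-emergent. If class means grade, a literal test of difference also counts 185 to 145, an improvement.

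**The case against.** The case for a lower rating is reasonable. Safety is descriptive, with no formal testing. Low readings stay in the listing with their abnormality flag and in the by-visit minimum. Clinically significant values must be recorded as adverse events (Protocol 8.5.4), and an internal committee reviews unblinded safety data. With 25 subjects and four scheduled readings there are about 25 × 4 = 100 scheduled readings per parameter, which can be read by eye. SAP section 1 puts technical derivations in a separate document not seen here, so the actual programming is unknown. All of this stands, and it limits the consequence. It does not make the two tables right, and a derivation document should not have to contradict the SAP to produce correct output.

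On the details:

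- Four of the six examples use pulse and rest on applying the heart-rate row to it. The systolic and diastolic examples do not.
- For weight, only the decrease direction is lost in practice, although the text has no change rule at all.
- In 6.3.4.4, direction is arguably the more natural reading because the wording closely follows the non-graded laboratory rule. That is the reading under which H2 to H4 is not counted as emergent, so clarification is still needed. The effect is confined to the frequency table: with shift-table categories taken from Appendix II, as 6.3.4.3 implies, H2 to H4 still shows there.

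**Conclusion.** The concern holds and should be fixed. Programmed as written, a subject with a low reading and any non-low reading after first dose appears as normal or high on the post-baseline side of the shift table, and is not counted as low in the treatment-emergent frequency table. A subject who is low throughout is shown at the mildest low grade reached. High grades on actual value are selected correctly, so the error always understates low abnormalities.

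The result follows from the text and needs no assumption about data. The one reading assumption is that the heart-rate row of Appendix II applies to pulse; without it the defect remains for both blood pressures and temperature. How many subjects are affected depends on the frequency of low readings, which the documents do not give. Baseline categories, listings, by-visit statistics and adverse events are not affected.

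**What to change.** - **SAP 6.3.4.5.** Define the worst case separately by direction: lowest post-baseline value for L grades, highest for H grades. Count a subject in both directions if both occur, as 6.3.2.7 does for non-graded laboratory results. Apply the tie rule to each direction.
- **Weight.** Add a worst case for change from baseline: largest decrease and largest increase.
- **SAP 6.3.4.4.** Adopt the graded-laboratory wording of 6.3.2.6: treatment-emergent if the grade is higher than at baseline or the direction changes. This captures H2 to H4 and leaves out H4 to H2.
- **Pulse.** State that the heart-rate row of Appendix II applies to pulse rate, if that is intended.

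The cost is wording in two SAP sections, one clarifying line on pulse, and a small change to the derivation and the two table programs before database lock. No new data are needed.
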